3.3.2 Inclusion Criteria

Identification of individuals appropriate for the study

Eligible patients will meet the following criteria:

- Clinical or molecular identification of Aicardi Goutières Syndrome including the following features
 - CSF or blood markers suggesting elevations of markers of interferon activation including CSF pleocytosis, elevation of interferon, and/or neopterin and tetrahydrobiopterin elevations
 - Evidence of neurologic disease on neuroimaging including intracranial calcifications and or a leukoencephalopathy
 - Clinical features of disease including features such as microcephaly, subacute encephalopathy, myopathy, spastic diplegia, skin involvement, autoimmune hepatitis, hematologic abnormalities
 - OR have documented mutations felt to be pathogenic in an AGS associated gene.
- Are ≥1 month of age.
- Are \geq 4.5 kg in body weight.
- Females after menarche must have a negative urine/serum pregnancy test and must use an acceptable method of contraception, including abstinence, a barrier method (diaphragm or condom), Depo-Provera, or an oral contraceptive, for the duration of the study.
- o Parental/guardian permission (informed consent).

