 - An estimated glomerular filtration rate (eGFR) based on the most recent available serum creatinine of <40 mL/min/1.73 m² if greater than 2 year of age. eGFR will be calculated using the *Bedside Schwartz Equation:* eGFR (mL/min/1.73 m²) = (0.413 x height) / S_{Cr}, with height measured in cm, and serum creatinine (S_{Cr}) in units of mg/dL.
 - Children with an eGFR of <40 mL/min/1.73 m² will not be enrolled, unless <24 months of age in which case a cut off of <30 ml/min/1.73 m2 will be used due to age-based differences in normal eGFR. Normal eGFR of <60 ml/min/1.73 m² is common in children <12 months, and a normal eFGR <40 ml/min/1.73 m² is common in infants <3-6 months.
 - The creatinine should be measured using the IDMS (Isotopic Dilution Mass Spectrometry) technique to monitor the eGFR if available. Other methods are allowed but are not preferred. Laboratory testing using other methods will not be used to monitor the eGFR.
- Have any of the following specific Hematologic abnormalities on screening laboratory tests (Appendices 10, 11, 12):
 - Hemoglobin <7 mg/dL (70 g/L). In infants <2 mo of age, 8 mg/dL will be used as a threshold
 - Neutropenia (absolute neutrophil count [ANC] <500 cells/µL)
 - CD4 <250 cell/µl on lymphocyte subset testing (where Absolute CD4 count=Absolute CD3/CD4 count=CD3/CD4 count=CD4 count=Absolute CD3+CD4+ cells)
 - Thrombocytopenia (platelets <30,000/µL). Patients who are on

anticoagulation or having a history of life-threatening bleeding should be excluded if platelet count is <50,000/µL

- Have any of the following infectious risks:
 - Evidence of active infection, at the time of entry or during the screening period, that in the opinion of the investigator, would pose an unacceptable risk for participating in the study
 - Ongoing or incompletely treated severe or systemic infection, excluding cellulitis/osteomyelitis that is felt to be attributable to AGS
 - Have had symptomatic herpes zoster infection within 12 weeks prior to entry or during the screening period
 - Have a history of disseminated/complicated herpes zoster (for example, multidermatomal involvement, central nervous system involvement or systemic involvement including hepatitis or pneumonitis)
 - Have a history of active hepatitis B, hepatitis C, or human immunodeficiency virus (HIV)
 - Have had household contact with a person with active tuberculosis (TB) and did not receive appropriate and documented prophylaxis for TB

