- Have screening laboratory test values outside the reference range for the population or investigative site that, in the opinion of the investigator, pose an unacceptable risk for the patient's participation in the study and are not attributable to AGS.
- Have screening thyroid-stimulating hormone and/or thyroxine values outside of the laboratory's reference range and are assessed to be clinically significant. If results are available from testing within 1 month, then the patient will not have to be retested. Patients who are receiving thyroxine as replacement therapy may participate in the study provided stable therapy has been administered.
- Have evidence of active or latent TB as documented by a positive purified protein derivative (PPD) test (≥5 mm induration between approximately 2 and 3 days after application, regardless of vaccination history), medical history, and chest x-ray at screening. The patient may also have a QuantiFERON®-TB Gold test. If the test is positive or indeterminate, the patient may undergo evaluation including a CXR and PPD and assessed for likely risk of active tuberculosis infection. In infants < 12 months of age, maternal and paternal testing can be used instead of testing the patient. Risk for TB will also be assessed using validated questions from The Red Book: Report of the Committee on Infectious Diseases (see below).

Validated Questions for Determining Risk of LTBI in Children in the United States

- Has a family member or contact had tuberculosis disease?
- Has a family member had a positive tuberculin skin test result?
- Was your child born in a high-risk country (countries other than the United States, Canada, Australia, New Zealand, or Western and North European countries)?
- Has your child traveled to a high-risk country? How much contact did your child have with the resident population?

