9.4.2.2.3 Anemia

Decreases in hemoglobin levels to less than 8 g/dL were reported in baricitinib clinical trials. CBC will be checked in individuals with ongoing treatment with baricitinib according to the study schedule and management of laboratory abnormalities will be performed according to Appendix 11. We will avoid initiation, decrease (Appendix 14) or interrupt baricitinib treatment in patients according to Appendix 11. Discussion with the study staff included in the Dysregulated Immune Response Team will help to determine if this complication is caused by AGS (see Appendix 11 for guidance). Testing will be performed as detailed in Appendix 11 and prophylaxis for individuals with abnormal values will be implemented as discussed in this section.

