Appendix 11. Management of Anemia

Exclusion criteria specific to anemia:

- Hemoglobin <7 mg/dL (70 g/L) will not be enrolled
- Hemoglobin <8 mg/dl will be used as a threshold in infants <2 months
- Patients not meeting criteria can follow protocols for further diagnosis and management and be reconsidered for enrollment at a later time

Criteria for consideration of drug tapering and discontinuation:

- Patients who develop a hemoglobin (Hg) of <7gm/dl*, should be transfused PRBCS as per institutional practice and a post transfusion Hg be measured weekly.
- Patients who develop a hemoglobin (Hg) of <7gm/dl* within <4 weeks of the transfusion should taper baricitinib to next dose increment (e.g. 2 mg tid to 2 mg bid) and be transfused PRBCS as per institutional practice and a post transfusion Hg be measured weekly.
- Patients who develop a hemoglobin (Hg) of <7gm/dl* within <4 weeks of the transfusion should taper baricitinib to next dose increment (e.g. 2 mg bid to 1 mg bid) and be transfused PRBCS as per institutional practice and a post transfusion Hg be measured weekly.
- If hemoglobin (Hg) of <7gm/dl* after two dose reductions, baricitinib should be tapered to cessation.
- Patients who develop a hemoglobin <5gm/dl at any time should taper baricitinib to cessation and be removed from protocol therapy*.
- Patients may dose escalate in a stepwise fashion after Hg>8gm/dl for >4 weeks.

* if acute blood loss in the context of GI bleeding, surgery, documented immune mediated hemolysis or anemia or an accident is the cause of the acute anemia, treatment of the underlying cause prior to drug tapering is warranted prior to drug tapering. Hemoglobin <8 mg/dI will be used as a threshold in infants <2 months. For patients who have been taking baricitinib for > 2 weeks and develop >50% drop in hemoglobin from baseline should have following work-up at minimum: CBC, reticulocyte count, LDH, haptoglobin, DAT, C5b-9, review of peripheral blood smear. Consider consultation with pediatric hematologist.

Management of anemia

- When these hematologic abnormalities occur, clinical management recommendations above will be shared with the local team in the form of a letter via email or fax, to enable the clinical team caring for the patient to use these best practices. The investigative team will retain decision making about drug discontinuation based on the above recommendations.

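### The hemoglobin exclusion limit is printed in mg/dL instead of g/dL, 1000-fold below its own bracketed value, and the infant limit appears only in the wrong unit

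*Combined protocol and SAP*

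**What the plan says.** The hematologic exclusions in section 3.3.3 state: "Hemoglobin <7 mg/dL (70 g/L). In infants <2 mo of age, 8 mg/dL will be used as a threshold".

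The exclusion list in Appendix 11 (Management of Anemia) repeats both limits: "Hemoglobin <7 mg/dL (70 g/L) will not be enrolled" and "Hemoglobin <8 mg/dl will be used as a threshold in infants <2 months". The footnote to the Appendix 11 rules for patients on treatment gives the infant limit again: "Hemoglobin <8 mg/dI will be used as a threshold in infants <2 months. For patients who have been taking baricitinib". The final character of the unit there is probably a misread letter l and has no bearing on the point.

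The other hemoglobin figures use the correct unit. The Appendix 11 rule for patients on treatment begins "Patients who develop a hemoglobin (Hg) of <7gm/dl*, should be transfused PRBCS as per institutional practice", and the neighbouring rules (below 5 for cessation, above 8 for re-escalation) are also in gm/dl. Section 9.4.2.2.3 says: "Decreases in hemoglobin levels to less than 8 g/dL were reported in baricitinib clinical trials".

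**The concern.** The general limit contradicts itself: the value in mg/dL and the value in g/L on the same line cannot both hold. The infant limit has the same wrong unit in all three printings and no second value to correct it.

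These limits decide who may receive baricitinib. Section 4.4.1 requires the enrollment criteria to be applied strictly as written. Through the footnote, the infant limit also modifies the rules that trigger transfusion and dose taper, and section 8.8 directs staff to the appendices. Appendix 11 adds that its management recommendations will be sent by letter to local clinical teams, so the wrong unit could reach clinicians outside the study.

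Other exclusions cover the gap only in part. The general laboratory exclusion in section 3.3.3 applies to values that "pose an unacceptable risk for the patient's participation in the study and are not attributable to AGS", and section 8.4.1 lists anemia among the common complications of AGS. The overall-health exclusion can cover AGS-related anemia, but it rests on the investigator's opinion.

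**Working it through.** **Conversion.** 1 g = 1000 mg and 1 dL = 0.1 L. So a value x in mg/dL equals x / 1000 / 0.1 g/L, and a value x in g/dL equals x / 0.1 g/L.

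**General limit (section 3.3.3 and Appendix 11), printed as 7 mg/dL with 70 g/L in brackets.**
- As printed: 7 / 1000 / 0.1 = 0.07 g/L. The bracketed 70 g/L is not reproduced.
- Mismatch: 70 / 0.07 = 1000.
- Read as g/dL: 7 / 0.1 = 70 g/L, which matches the bracket exactly.
- In reverse: 70 g/L × 1000 × 0.1 = 7000 mg/dL.

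**Infant limit (section 3.3.3, and Appendix 11 exclusion list and footnote), printed as 8 mg/dL with no bracket.**
- As printed: 8 / 1000 / 0.1 = 0.08 g/L.
- Read as g/dL: 8 / 0.1 = 80 g/L.
- Ratio: 80 / 0.08 = 1000.

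**Count of affected figures.**

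| Place | General limit | Infant limit |
|---|---|---|
| Section 3.3.3 | 1 | 1 |
| Appendix 11, exclusion list | 1 | 1 |
| Appendix 11, footnote | – | 1 |
| Total | 2 | 3 |

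This gives 2 + 3 = 5.

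**Could another passage correct the infant figure?** Two places give 8 in a correct unit, but neither states the infant limit. The figure above 8 gm/dl in Appendix 11 is the level at which the dose may be raised again, and the figure in section 9.4.2.2.3 describes other baricitinib trials.

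**Could it be an artefact of reading the PDF?** This is unlikely. The wrong unit attaches to the same two limits in two separate sections, while the adjacent gm/dl rules in Appendix 11 come through intact.

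**Who is exposed.** Section 3.3.2 requires that patients "Are ≥1 month of age" and weigh at least 4.5 kg. The infant limit therefore covers ages 1 to under 2 months, and the footnote can apply to a given infant for about one month at most. Patients rolling over from the compassionate use study need not meet the eligibility criteria (section 3.3.1), so the exclusion limits concern new enrollees.

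In Table 1 of the protocol, 6 of 35 patients had a grade 1 hemoglobin abnormality before study and none had a higher grade. On study, 1 of 35 reached grade 3. If those grades correspond roughly to the limits of 7 and 8 g/dL, the limits would seldom be reached. That is an assumption, because the table gives neither the cut-off for each grade nor a breakdown for young infants.

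**The case against.** The strongest reply is that this is a typing slip that corrects itself. The general limit carries 70 g/L in both places, and no screened patient could have a hemoglobin of 7 or 8 mg/dL, so nobody could apply the limit as printed. The infant figure in section 3.3.3 directly follows the 70 g/L value and is plainly a small step up from 7. In Appendix 11 the footnote is attached by asterisk to rules printed in gm/dl, which supply the unit. No rival reading exists. Transfusion is left to institutional practice, and the appendix says that departures by the treating clinician are not protocol deviations.

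Most of this stands. The intended values are clear, and the error is unlikely to mislead an experienced clinician. The point about transfusion also stands: for patients on treatment, the decision that stays with the study team is taper and discontinuation. The reply does not make the text right. Enrollment and taper remain study decisions made against these limits, and the infant value still has to be inferred from its surroundings.

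**Conclusion.** The concern holds. Five printed hemoglobin figures carry mg/dL where g/dL is evidently meant, an error of exactly 1000-fold in each. For the general limit the intended value is certain, because 7 g/dL equals the bracketed 70 g/L. For the infant limit, 8 g/dL (80 g/L) is an inference, though a safe one.

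The consequence is minor. It touches eligibility and safety wording only, the infant group is narrow, and readers will probably supply the right unit. It is an editorial correction to a written safety limit.

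**What to change.** Replace mg/dL with g/dL in the five figures: both in section 3.3.3, both bullets of the Appendix 11 exclusion list, and the Appendix 11 footnote. Print the infant limit as 8 g/dL (80 g/L) each time, so that it has its own cross-check. Leave the gm/dl rules for patients on treatment as they are.

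The cost is five unit corrections in the text at the next amendment, with no change to design, data collection or analysis.

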4 STUDY PROCEDURES

4.1 Unforeseeable emergency events

In some circumstances, unforeseeable events, such as public health emergencies, states of emergency related to civil unrest, or weather emergencies, or individual health emergencies (affecting the patient or a caregiver), may create situations where it is unsafe for patients and their families to travel to the study site for in-person assessments. In that case, the visit will be conducted using video operations. The changes from an in-person evaluation, including differences to the study outcome collection, will be reported as a minor protocol deviation to the IRB at the time of continuing review.

4.2 Pre-screening period

The pre-screening period is applicable only to subjects not transferred from the JAGA Compassionate Use study (CHOP IRB Study #13205). The pre-screening period is a period from 2 weeks to 6 months during which the study will be discussed with the patient and caregivers. During this time, the study team may discuss the study with patients and families, and records of clinically indicated studies will be collected to help determine potential eligibility during the screening process. Individuals will undergo this pre-screening period if insufficient information about prior clinical care is available to the study team, for example, if their clinical care is received outside of the regional area. As part of the pre-screening period, patients or their guardians will undergo telephone consent, to explain the purpose and procedure of the study. Formal written consent will be obtained at Visit 1. During this period, blood and urine will be collected and daily diaries completed.

4.3 Screening Visit

Screening (Visit 1) is applicable only to subjects not transferred from the JAGA Compassionate Use study (CHOP IRB Study #13205). The screening visit is a 2- to 28day period beginning at Visit 1. After receiving written informed consent from the patient's parent or a legal guardian (hereafter, "parent" refers to "parent or legal guardian"), patients will be assigned a patient number and will be considered entered into the study and study procedures may begin. Entry procedures will be performed per the Study Schedule (Appendices 1 and 2). During the screening period, patients must complete at least 14 days of diary entries before receiving the first dose of baricitinib (refer to the Patient Diary and Diary Score section below and Appendices 5 and 6). Current use of concomitant medications and reasons for use will also be collected on the eCRF, as well as start and stop dates. Particular note will be made of medications that are contraindicated (see Section 3.4.2) and which require dose adjustment (see Section 4.4).

4.4 Study Treatment Phase

4.4.1 Enrollment

Consent

Written informed consent from the patient/patient's parent or a legal guardian will be obtained in person by the study investigators prior to any study procedure, with the exception of blood and urine tests, and daily diaries, which may be completed from the pre-screening period, after verbal consent.

For the patients transferred from the JAGA Compassionate Use study (CHOP IRB Study #13205), written informed consent from the patient/patient's parent or a legal guardian will be obtained by the study investigators prior to any study procedure completed as part of this investigator-initiated study.

Additionally, all the JAGA subjects (including the patients who do not consent and transition to the investigator-initiated JAK inhibitor treatment in AGS study will be asked to sign a consent form to allow for their data collected as part of the compassionate use program to be used for data analysis as part of the investigator-initiated study. The JAGA subjects who do not transition to the investigator-initated study will sign a separate consent form while the subjects who transition will be re-consented with a revised informed consent form including mention of this data transfer. Statistical considerations of this data transfer are detailed in Section 6.

Inclusion criteria

Entered patients are eligible for enrollment into the study (that is, eligible to receive baricitinib) only if they meet inclusion criteria (Section 3.4.1) at the time of Visit 2 and don't meet the exclusion criteria listed in Section 3.4.2.

Exclusion from Study Enrollment

Entered patients are ineligible for enrollment (that is, ineligible to receive baricitinib) and should be discontinued from the study if they meet any of the exclusion criteria listed in Section 3.4.2.

Patients who are entered, but do not meet enrollment criteria, should be discontinued from the study. These patients can be re-entered into the trial (that is, be reconsented) if the investigator believes that the patient might meet enrollment criteria at a future date, taking into consideration the volume of blood required for rescreening. Patients will receive treatment as clinically indicated for infections regardless of treatment decisions for baricitinib.

Rationale for Exclusion of Certain Study Candidates

Exclusion Criterion excludes individuals with concomitant medical conditions that increase the risk for their participation in the study, who may not be compliant with study-related procedures or whose participation in the study may introduce bias.

Discontinuation of patients after enrollment if criteria are not met

The criteria for enrollment must be followed explicitly. If a patient who does not meet enrollment criteria is inadvertently enrolled, that patient should be discontinued from the investigational product, but may be allowed to continue in the study in order to provide the follow-up data.

4.4.2 Initial Treatment and Dose Escalation

Baricitinib will be dosed by patient age, weight range and eGFR. See Appendix 3 for the dosing schedule for patients with eGFR \geq 60 mL/min/1.73 m² or normal eGFR for patients age <24 months (eGFR \geq 60 mL/min/1.73 m²). eGFR will be calculated using the *Bedside Schwartz Equation:* eGFR (mL/min/1.73 m²) = (0.413 x height) / S_{Cr}, with height measured in cm, and serum creatinine (S_{Cr}) in units of mg/dL. The creatinine should be measured using the IDMS (Isotopic Dilution Mass Spectrometry) technique to monitor the eGFR if available. Other methods are allowed but are not preferred. Laboratory testing using other methods will not be used to monitor the eGFR. Tolerance will be judged by stability or improvement in hematology and chemistry laboratory test results collected as specified in Study Schedule (Appendices 1 and 2). See Appendix 4 for the dosing schedule for patients with eGFR 30 - <60 mL/min/1.73 m²).

Patients must receive a dose for at least 72 hours before a dose escalation can occur. Safety laboratory data will be assessed according to the Study Schedule (Appendices 1 and 2).

Every effort should be made to follow the dose escalation schedule shown in Appendices 3 and 4. However, if a patient's condition warrants an accelerated dose escalation schedule, dose reduction, interruption, or discontinuation, this may be allowed after review of the patient's clinical data and consultation with the subinvestigators. Additionally, in the event of AEs possibly attributable to the study drug, the dose may need to be reduced. These decisions should be taken following documented consultation, and agreement between the investigator and subinvestigators, and approval from the IRB prior to initiating the dose modification. Only in emergency situations will the investigator take subsequent dose restarts or increments after review of clinical data, documented agreement between the investigator and subinvestigators, and notification of the IRB.

Attention will be given to concomitant medications, in particular those that are exclusion criteria (Appendix 16).

Where needed, clinical pharmacists will be contacted about the need for dose adjustment and for guidance related to concomitant therapies that must be used with caution.

In the event that it is necessary to contact a clinical pharmacist, the study team can page the 24/7 on-call clinical pharmacist.

Pharmacokinetic Sampling: Blood samples will be collected to determine baricitinib concentrations. Samples will be collected after beginning baricitinib therapy and at each dose increase at the time points shown in the Study timeline and may be collected at each study visit for safety monitoring. In these cases, PK sampling will occur at least 72 hours after dosing changes or at the next visit. PK testing may include a single measurement at 1.5 hours, or a full PK series at baseline, 1.5 hours and 4 hours post dose, and may include several doses during the day (eg morning and afternoon dose). For PK series, an IV will be placed. For single PKs, these will be drawn with the safety laboratory monitoring. PK samples may be banked for later analysis. As PK data become available, dosing adjustments may be required. Finally, changes in a subject's weight or renal function may require dose changes as the individual falls within different categories in the tables in Appendices 3 and 4. For example, this may occur in a child under 1 year of age with rapid weight gain.

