3.1.2 Additional subjects

3.1.2.1 Screening Phase

Participants will be recruited by advertisement via testing laboratories, family advocacy organizations, self-referral, or participation in a clinical leukodystrophy program. Patients' families will be first contacted by non-study personnel to discuss the possibility of participating in a clinical trial. If the patient is also a patient of the investigators, study participation will be discussed with the Medical Monitor. Should the family be interested, patients and families will be invited to contact the investigative team to discuss participation and ICF documents will be shared with the family. Should the family continue to be interested, the family will be invited to visit CHOP.

Potential subjects will be screened using the protocol inclusion and exclusion criteria. Potential subjects can also be pre-screened over the phone. The pre-screening period is described in Section 4.2. As part of the pre-screening period, patients or their guardians will undergo telephone consent, to explain the purpose and procedure of the study. Formal written consent will be obtained at Visit 1. Medical records will be collected for verification of study eligibility, including mutation status, after release of information and after verbal consent for screening. Parental/guardian permission (informed consent) will be obtained prior to any study related procedures being performed. Physical examination, echocardiogram, EKG, CXR, baseline neurologic function testing, and blood samples will be drawn to confirm eligibility based on clinical laboratory parameters. Additional results of blood tests for hematologic, liver, and metabolic parameters will be performed on a research basis for screening purposes. Females after menarche will have a urine pregnancy test. Eligible patients will be enrolled and initiated on intervention, baricitinib, using openlabel treatment, and according to established dosing regimens for weight and eGFR based on age (Appendices 3 and 4). Regular evaluations for safety and efficacy (Appendices 1 and 2) will be performed while on study intervention (see section 4).

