4.5 Continuing treatment

4.5.1 Continuing treatment for patients transferred from the JAGA Compassionate Use study

After consent to the investigator-initiated JAK inhibitor treatment in AGS study, transferred patients will undergo review of the patient's clinical condition, AEs, and blood tests for safety by the Principal Investigator. Safety laboratory assessments will be reviewed by the investigator along with a copy of the patient's diary, AEs and concomitant medications. If the patient is responding adequately to treatment (average diary score <0.5) or reduction in average diary score, the patient will continue receiving baricitinib therapy with follow-up appointments according to the Study Schedule (Appendices 1 and 2), based on the timelines of the most recent study visit on the JAGA Compassionate Use study (CHOP IRB Study #13205). If the patient is responding to treatment, but has not yet reached symptom control, dose escalation may be performed as discussed above and in Appendices 3 and 4. Once the patient has reached a stable dose of baricitinib, the same total dose may be administered as equal or unequal divided doses (administered up to 4 doses in a day [24 hours]).

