BID = twice daily, eGFR = estimated glomerular filtration rate, QID = 4 times daily, TID = 3 times daily.

a If there was a change in the patient's weight during the study, this would place the patient in a different weight range.

b Based on adult patient data as there is little data available in pediatric patients.

c. For the purposes of this protocol, we will define age based parameters for eGFR as follows: Normal renal function not requiring dose adjustments if: >12 months: At least a GFR of >60 ml/min/1.73 m2. <12 months: A GFR of >40 ml/min/1.73 m2. Patients will be excluded from enrollment if baseline eGFR was <30 ml/min/1.73 m2

The creatinine should be measured using the IDMS (Isotopic Dilution Mass Spectrometry) technique to monitor the eGFR if available. Other methods are allowed but are not preferred. Laboratory testing using other methods will not be used to monitor the eGFR.

The population PK analysis was updated including data from 71 juvenile and adolescent patients with Chronic Atypical Neutrophilic Dermatosis with Lipodystrophy and Elevated Temperature (CANDLE), CANDLE related disorders, STING-associated vasculopathy with onset in infancy (SAVI), and Aicardi-Goutières syndrome (AGS). The analysis has shown that while kidney function, as expressed by estimated GFR, is a statistically significant patient cofactor of the PK characteristics of baricitinib in this multi-disease patient population, the effects of eGFR on the kinetics of this patient population were not clinically relevant as they relate to dosing and did not support dose adjustment for patients with eGFR less than 120 mL/min/1.73 m².

Appendix 4. Dose Escalation Schedule for Patients with eGFR 30- <60 mL/min/1.73 m2 or for Age <24 Months with abnormal eGFR (see footnote below^c)

If a change in the patient's weight during the study would place the patient in a different weight range changes over time are permitted.

		Morning Dose	Noon Dose	Afternoon Dose	Evening Dose	Total Daily Dose	Dosing Frequency
eGFR 30 - < 60 mL/min/ *	1.73 m ^{2b}						I
10-< 20 kg	Initial	1 mg	1 mg	0 mg	1 mg	3 mg	TID
	Escalation 1	1 mg	1 mg	1 mg	1 mg	4 mg	QID
20-< 40 kg	Initial	2 mg	-	_	1 mg	3 mg	BID
	Escalation 1	2 mg	_	_	2 mg	4 mg	BID
≥ 40 kg	Initial	2 mg	_	_	2 mg	4 mg	BID
	Escalation 1	3 mg	-	_	3 mg	6 mg	BID

BID = twice daily, eGFR = estimated glomerular filtration rate, QID = 4 times daily, TID = 3 times daily.

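### Section 4.4.2 sets normal eGFR under 24 months at 60 or more, which contradicts footnote c of the dose tables for infants under 12 months with eGFR above 40 and below 60

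*Combined protocol and SAP*

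**What the plan says.** Section 4.4.2 gives two routes into Appendix 3. One is eGFR of 60 or more. The other is "normal eGFR for patients age <24 months (eGFR" of 60 or more, with the threshold in the parenthetical identical to the first. The section then directs the reader: "See Appendix 4 for the dosing schedule for patients with eGFR 30 - <60 mL/min/1.73". No age condition is legible in that sentence.

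Footnote c, printed under both Appendix 3 and Appendix 4, sets age-based limits for the whole protocol. It lists what counts as "Normal renal function not requiring dose adjustments if", and the infant limit is "<12 months: A GFR of >40 ml/min/1.73 m2". Above 12 months it uses 60.

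Two other places bear on which text is right. Section 3.1.2.1 says patients are dosed "according to established dosing regimens for weight and eGFR based on age (Appendices 3 and 4"). Section 3.3.3 says that a normal eGFR below 60 "is common in children <12 months", and sets the enrolment floor under 24 months at 30.

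**The concern.** An age exception whose threshold equals the general threshold has no effect. Section 4.4.2 evidently means to treat young children differently, but its number does not do so. Footnote c does.

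The threshold selects the dose table. An infant under 12 months with eGFR of, say, 50 has normal function by footnote c and belongs in Appendix 3. By Section 4.4.2 the same infant does not qualify for Appendix 3 and, on the sentence as it reads, goes to the reduced-dose table. Such infants are eligible: Section 3.3.2 admits patients from 1 month of age and 4.5 kg. Section 1.1 also argues that benefit is likely greatest when treatment starts early, so an unintended reduction in infants runs against the protocol's own rationale.

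**Working it through.** No figure in the plan needs reproducing. The check is to apply both rules to the same patients and then read off the doses.

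**Rules as applied**

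- Section 4.4.2: eGFR ≥60 goes to Appendix 3; 30 to <60 goes to Appendix 4; age makes no difference.
- Footnote c, under 12 months: eGFR >40 goes to Appendix 3; 30 to 40 goes to Appendix 4.
- Footnote c, from 12 months: eGFR ≥60 goes to Appendix 3; 30 to <60 goes to Appendix 4.

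Footnote c leaves two boundaries loose. It asks for at least a value above 60, and it does not assign exactly 12 months. I take eGFR of exactly 60 as normal and exactly 12 months as belonging to the older group.

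**Which table each rule gives**

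| Age | eGFR | Section 4.4.2 | Footnote c |
|---|---|---|---|
| 6 months | 30, 35, 40 | Appendix 4 | Appendix 4 |
| 6 months | 41, 45, 50, 55, 59 | Appendix 4 | Appendix 3 |
| 6 months | 60, 61 | Appendix 3 | Appendix 3 |
| 18 months | 30 to 59 | Appendix 4 | Appendix 4 |
| 18 months | 60, 61 | Appendix 3 | Appendix 3 |

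On a grid of eGFR 30 to 69.5 in steps of 0.5, at ages 6, 11, 12, 18, 23 and 36 months, the rules disagree only at 6 and 11 months, and only from 40.5 to 59.5.

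**Dose difference at 10 to <20 kg**

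| Step | Appendix 3 | Appendix 4 | Difference | Appendix 4 ÷ Appendix 3 |
|---|---|---|---|---|
| Initial | 6 mg/day | 3 mg/day | 6 − 3 = 3 mg/day | 3/6 = 50% |
| Escalation 1 | 8 mg/day | 4 mg/day | 8 − 4 = 4 mg/day | 4/8 = 50% |

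The escalated Appendix 4 dose (4 mg/day) is still below the Appendix 3 starting dose (6 mg/day), so escalating within Appendix 4 does not close the gap.

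**Below 10 kg.** Appendix 3 has a row for 5 to <10 kg (3 then 4 mg/day). Appendix 4, in the text available, has none. A row may have been lost when the table was read from the PDF, so I compute no difference there.

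**Who is exposed.** The disagreement is not confined to infants starting drug. Section 4.4.2 says that changes in weight or renal function can move a subject between table categories, and gives a child under 1 year with rapid weight gain as an example. Section 4.5.1 says that for a transferred patient who is responding adequately, "the patient will continue receiving baricitinib therapy with follow-up appointments"; but it also allows transferred patients who lack symptom control to escalate under the same appendices. For any one infant the disagreement ends at 12 months of age.

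**The case against.** The strongest reply is that the protocol already says which text governs. Footnote c is worded as protocol-wide and sits under both tables, where a prescriber reads the dose. Sections 3.1.2.1 and 7.1.3 and Section 4.4.2 itself all defer to Appendices 3 and 4. This stands as evidence of which text is wrong: these are not two equal rules, but one sound definition and one faulty parenthetical. It does not remove the contradiction, because Section 4.4.2 is the section that tells the reader which table to open.

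Second, the two-fold difference needs an infant under 12 months who weighs at least 10 kg and has eGFR above 40 and below 60. Section 9.4.2.1.7 notes decreased growth in AGS, Section 8.4 lists feeding failure as an expected complication, and Section 3.3.3 places the lowest normal eGFR values in the youngest infants. This stands: few infants are likely to meet all three conditions.

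Third, the consequence is limited. The error gives a lower dose, not a higher one. Section 4.5.2 allows escalation when symptoms are not controlled. Section 4.4.2 allows accelerated escalation after consultation, PK-driven adjustment and pharmacist advice. The population PK note under both tables says eGFR effects "were not clinically relevant as they relate to dosing". This also stands, although the protocol still keeps a reduced-dose table.

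Fourth, the Appendix 4 sentence in Section 4.4.2 ends with a bracket that was never opened, so an age clause may have been lost. That weakens any claim about that sentence. It does not touch the parenthetical, whose threshold of 60 is legible.

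A reader might infer that dosing is contradictory for all children under 24 months, or that infants generally would receive half the intended dose. The documents support neither: the rules agree from 12 months, and the halving is shown only at 10 to <20 kg.

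**Conclusion.** The point holds as a minor internal inconsistency. The parenthetical in Section 4.4.2 is wrong: it duplicates the general rule and contradicts footnote c, which Sections 3.1.2.1 and 3.3.3 support. For infants under 12 months with eGFR above 40 and below 60, Section 4.4.2 withholds Appendix 3 and, as its Appendix 4 sentence reads, gives the reduced table. At 10 to <20 kg that is 50% of the footnote c dose.

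This rests on reading exactly 60 as normal and exactly 12 months as the older group, and, for the routing into Appendix 4, on that sentence having no lost age clause. The documents give no distribution of infant weight or eGFR, so the number affected cannot be estimated.

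Three further inferences should be resisted. The titles of Appendices 3 and 4 are not a separate conflict, because both carry an age clause that refers to footnote c. The absent Appendix 4 row below 10 kg cannot be treated as a gap in the plan. Nothing here bears on the endpoint, analysis, power or results of the trial.

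**What to change.** Subject to confirmation by the sponsor's clinical and PK team:

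1. In Section 4.4.2, replace the parenthetical threshold for age under 24 months with the footnote c limits: above 40 under 12 months, and 60 or more from 12 months.
2. If the source text does not already say so, limit the Appendix 4 sentence in Section 4.4.2 to patients below that age-based normal: 30 to 40 under 12 months, and 30 to <60 from 12 months. Section 3.3.3 continues to govern enrolment.

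Optionally, and for consistency only, word the Appendix 4 title and its entry in the Section 8.8 list the same way.

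The cost is a wording amendment to two sentences, with two matching labels if wanted. It needs no extra procedures, visits or patients.
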